8.2.3 Reporting of Serious Adverse Events

All SAEs (as defined below) regardless of the suspected relationship to OTL-101, must be reported immediately (within 24 hours of the Investigator's knowledge of the event) to the pharmacovigilance contact specified at the beginning of this protocol. If the immediate report is submitted by telephone, this must be followed by detailed written reports using the SAE report form.

For subjects who are not geographically close to the clinical site who are clinically stable, post-transplant care may be transferred to the home physician provided the identified clinician agrees to assume this post-transplant monitoring. Any discharge from the clinical site and re-admission to the local site (second facility) would not meet the criteria for being reported as a serious adverse event.

An SAE is any AE that:

- Results in death,
- Is life threatening, that is any event that places the subject at immediate risk of death from the event as it occurred. It does not include an event that, had it occurred in a more severe form, might have caused death,
- Results of in-patient hospitalization or a prolongation of existing hospitalization, excluding admission for social or administrative reasons (see below),
- Results in a persistent or significant disability/incapacity, where disability is a substantial disruption of a person's ability to conduct normal life functions,
- Results in congenital anomaly/birth defect in the offspring of a subject who received OTL-101,
- Is an important medical event that may not result in death, be life threatening, or require hospitalization, but that, based upon appropriate medical judgment, may jeopardize the subject and may require medical or surgical intervention to prevent one of the outcomes listed in this definition. Examples of such medical events include allergic bronchospasm

PROTOCOL AMENDMENT 4: VERSION 5.0, 28 MARCH 2018

PAGE 72/130

requiring intensive treatment in an emergency room or at home, blood dyscrasias or convulsions that do not result in in-patient hospitalization, or the development of drug dependency or drug abuse.

In addition to the above criteria, any additional AE that the Sponsor or an Investigator considers serious should be reported immediately to the Sponsor and included in the corporate SAE database system.

- Hospitalization is defined as any in-patient admission (even if less than 24 hours). For chronic or long term in-patients, in-patient admission also includes transfer within the hospital to an acute/intensive care in-patient unit.
- Prolongation of hospitalization is defined as any extension of an in-patient hospitalization beyond the stay anticipated/required in relation to the original reason for the initial admission, as determined by the Investigator or treating physician. For protocol specified hospitalization in clinical studies, prolongation is defined as any extension beyond the length of stay described in the protocol. Prolongation in the absence of a precipitating, treatment emergent, clinical AE (i.e. not associated with the development of a new AE or worsening of a pre-existing condition) may meet criteria for "seriousness" but is not an adverse experience and thus is not subject to immediate reporting to the Sponsor.
- Preplanned or elective treatments/surgical procedures should be noted in the subject's screening documentation. Hospitalization for a preplanned or elective treatment/surgical procedure should not be reported as an SAE unless there are complications or sequelae which meet the criteria for seriousness as described above.

Any SAE must be reported immediately (within 24 hours), independent of the circumstances or suspected cause, if it occurs or comes to the attention of the Investigator at any time during the study period.

Any AE/SAE with a suspected causal relationship to OTL-101 administration occurring at any other time after completion of the study must be promptly reported. The following information is the minimum that must be provided to Sponsor's pharmacovigilance contact within 24 hours for each SAE:

- Study number
- Center number
- Subject number
- AE
- Investigator's name and contact details

The additional information included in the SAE form must be provided to the Sponsor or nominated representative as soon as it is available. The Investigator should always provide an assessment of causality for each event reported to the Sponsor. Upon receipt of the initial report, the Sponsor will ask for the Investigator's causality assessment if it was not provided with the initial report.

The Investigator should report a diagnosis or a syndrome rather than individual signs or symptoms. The Investigator should also try to separate a primary AE considered as the foremost untoward medical occurrence from secondary AEs which occurred as complications.

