3.5 Duration of Subject Participation

The study will consist of the following periods:

- Screening: approximately 2 months
- Bone marrow harvest of autologous cells: 1 day
- Manufacture and release of OTL-101: 30-45 days
- Pre-conditioning prior to transplant: 4 days
- OTL-101 administration: this may entail up to 4-6 weeks of in-patient stay, either at UCLA or the subject may be transferred from UCLA to a home hospital at 3-7 days post-transplant for the pursuit of subsequent hospitalization for up to 4-6 weeks.
- Post treatment follow-up: 2 years after the administration of OTL-101.

The total study duration for each subject is estimated to be up to 2 years and 4 months.

The study will start when the first subject has signed the informed consent form. Each subject's participation in the study will end at the time of his/her last visit, or death. The study will have ended after the last subject has completed the last study visit at 24 months post OTL-101 infusion, however the primary endpoints for this study will be overall survival and event free survival at 12 months post OTL-101 infusion.

On completion of their participation in this study, subjects will be invited and encouraged to participate in a registry for long term data collection according to guideline recommendations.

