5.1.6 Immediate Post-transplant Tests and Care (Visit 3)

These visits will be performed as part of the subject's hospital admission which commenced at the baseline visit (Visit 3). During the first month after administration of the OTL-101 treatment, the following tests will be performed on the day after treatment (Day 1) and then twice weekly thereafter.

These visits may be performed +/- 2 days from the scheduled date.

Post-transplant (Assessments G to M)

- Interval history (including routine review of systems, including infectious symptoms (e.g., fever), AEs and concomitant medications),
- Hematology (see [Table 3](#)),
- Biochemistry (see [Table 3](#)).

The subjects will be kept in hospital for close monitoring for up to 24 days post OTL-101 infusion. However, they may be kept in for longer if this is deemed clinically necessary and depending on the medical care they require (e.g. central venous catheter care, infections, protective isolation, nutritional support), the consequences of toxicity due to Busulfan, the engraftment of transduced cells, and immune reconstitution. Alternatively, for subjects who are not geographically close to the clinical site who are clinically stable, post-transplant care may be transferred to the home physician provided the identified clinician agrees to assume this post-transplant monitoring. The home physician will be asked to record all protocol specific assessments on a form provided. This data will be transmitted to the Investigator for data entry into the eCRF. Monitoring can be assured as either an in-patient or out-patient. In the latter case, the subject will stay in hospital for a minimum of 3 days after OTL-101 infusion at the investigational site treatment facility, before being transferred. This planned discharge and subsequent readmission to a second facility would not meet the criteria for being reported as a SAE.

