After the transplant, the subject will be maintained on prophylactic antibiotics and intravenous gamma-globulin replacement as needed and/or as per institutional procedures, and will be closely monitored. Any concomitant medication administered to the subject should be recorded in the eCRF. A subject will be readmitted to hospital when deemed clinically necessary. These reasons include, but are not limited to: fever and neutropenia, bacteremia, possible central venous access device infection, or other infections that require initial parenteral antibiotics, organ failure, extreme adverse social situations, and/or bleeding.

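### Section 8.2.3 exempts any discharge and local re-admission from SAE reporting where Section 5.1.6 exempts only the planned transfer, so an unplanned local admission caused by an adverse event can be misread as exempt

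*Protocol*

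**What the plan says.** Two protocol sections address the same situation. After infusion, a child who lives far from the single study site may have post-transplant care handed over to a physician near home.

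- Section 5.1.6 (Immediate Post-transplant Tests and Care) ends its description of the transfer with: "This planned discharge and subsequent readmission to a second facility would not meet the criteria for being reported as a SAE".
- Section 8.2.3 (Reporting of Serious Adverse Events) begins its paragraph with "For subjects who are not geographically close to the clinical site who are clinically stable, post-transplant care may be transferred to the home physician", and then states: "Any discharge from the clinical site and re-admission to the local site (second facility) would not meet the criteria for being reported" as an SAE.

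Section 8.2.3 goes on to list the SAE criteria, including in-patient hospitalization or its prolongation. It counts every in-patient admission as hospitalization, however short, and does not restrict this to the study hospital.

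**The concern.** Section 8.2.3 is the text that staff will consult when deciding whether to report. There the qualifier *planned* has gone and *any* stands in its place. The sentence can be read as a specific exception to the general hospitalization criterion that follows it. On that reading, a child followed at home and then admitted locally with an infection would not be reported on the strength of the admission. A child readmitted to the study site with the same illness would be.

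At stake are the 24-hour reports to the sponsor, the ongoing SAE review in protocol Section 3.6.2, and the SAE summaries in SAP Section 8.4.1.2. Transfer takes place early, soon after Busulfan conditioning, when admissions of this kind are foreseeable.

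**Working it through.** No figure in the plan bears on this point, so the check is a comparison of the texts.

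**1. What is exempted.**

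| | Section 5.1.6 | Section 8.2.3 |
|---|---|---|
| Setting | Stable, distant child; care handed to home physician | Same |
| Discharge exempted | The planned one | Any |
| Readmission exempted | The one following the planned discharge | Any to the local site |

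The settings match. Only the reach of the exemption differs.

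**2. Can the wider wording reach an unplanned admission?** Yes. Section 3.5 says "the subject may be transferred from UCLA to a home hospital at 3-7 days post-transplant", which describes a transfer from one hospital bed to another. Section 5.1.6 is broader: "Monitoring can be assured as either an in-patient or out-patient". A child transferred as an out-patient has no planned local admission, so a local admission during that follow-up would ordinarily be unplanned. It would still be a discharge from the clinical site followed by an admission to the local one. The requirement of clinical stability describes the child at handover and says nothing about later events.

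**3. Are such admissions expected?** Section 5.1.6 gives reasons for readmission that include "fever and neutropenia, bacteremia, possible central venous access device infection, or other infections that require initial parenteral antibiotics". It does not extend its exemption to them.

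**4. Does this collide with the SAE definition?** Section 8.2.3 keeps two kinds of admission out of the hospitalization criterion: those for social or administrative reasons, and preplanned or elective treatment without qualifying complications. A local admission for infection is neither. Under the definition it counts; under the literal exemption it does not. The section does not say which prevails.

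**5. What would still catch the event?**
- The life-threatening and important-medical-event criteria do not depend on admission.
- The sponsor or investigator may report any event that either considers serious.
- Section 8.2.2 requires adverse events seen by the child's general practitioner to be passed to the study site, on the same day if possible. It also requires the investigator to assess each adverse event against the SAE criteria.

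The first two depend on judgement. A short admission for fever and neutropenia, in a child not at immediate risk of death, might qualify clearly only through hospitalization, which is the criterion that the sentence blurs.

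**6. Scale.** Section 9.4 plans ten treated subjects. One subject whose only SAE went unreported would change the proportion with any SAE by 1/10, or 10 percentage points. This shows how sensitive the table is. It does not estimate how many subjects would be affected.

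**The case against.** The strongest reply is that the sentence closes a paragraph about moving stable children between facilities. It exempts that movement, not an illness that later causes an admission. The hospitalization criterion covers any hospital, and Section 8.2.3 requires every SAE to be reported whatever led to it. This is the better reading of the section as a whole. It stands against an inference that a reader might draw, namely that a local admission for febrile neutropenia or sepsis is not an SAE as the protocol is written. The documents do not support that. It does not remove the discrepancy: the duty to report SAEs applies once an event is classified, and classification is where the two statements disagree.

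The consequences are also limited. SAP Section 8.3.2.4 takes infections for the severe-infection endpoint from adverse event records, and SAP Section 8.4.3 summarizes infectious episodes separately, so both are less exposed. The stopping rules in protocol Section 3.6.1 do not depend on SAE status. The data safety monitoring board reviews emerging safety data generally. A comparison with children who stay in the study hospital is not clean either: they have no new admission, so the hospitalization criterion applies to them only through prolongation. The clean contrast is readmission to the study site against readmission to the local one.

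A reader might also assume transfer and readmission rates and compute a chance of losing SAEs. The documents give neither rate. Such a calculation would also have to assume that every local readmission is misread as exempt and meets no other SAE criterion. Nothing in the documents supports that.

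**Conclusion.** The inconsistency between Sections 8.2.3 and 5.1.6 is real and should be corrected. The wording of Section 8.2.3 can be taken to exempt an unplanned local admission caused by an adverse event, contrary to Section 5.1.6 and to the hospitalization criterion in its own section. The result would be uneven 24-hour reporting and uneven SAE counts, depending on how the sentence is read and which hospital admits the child. It is not a rule that takes these events out of SAE status, and other provisions would recover many of them.

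The size cannot be estimated from the documents. The conclusion rests on the wording alone, and on one practical assumption: that some staff would read the sentence by itself and apply it as a specific exception.

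**What to change.** In Section 8.2.3, bring the exemption back to that of Section 5.1.6: only the planned discharge and subsequent readmission to the second facility, not prompted by an adverse event, is exempt. The last condition is an addition for clarity. It should concern the reason for the move, not require that the child has had no adverse event at all, since minor events after conditioning would otherwise void the exemption for an ordinary planned transfer.

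Add one sentence stating that any adverse event leading to or prolonging an admission, at either facility, is judged by the ordinary SAE criteria.

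Optionally, before each analysis, compare the adverse events and any admissions reported by home physicians with the SAE listing. Section 5.1.6 says only that the home physician's form records protocol-specific assessments, so the form may need a field for admissions.

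The cost is a sentence or two in the next amendment, possibly a few more SAE reports, and a small data check if the option is taken. No treatment or clinical rule changes.

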8.2.4 Pregnancy

Pregnancy itself is not regarded as an AE unless there is a suspicion that OTL-101 has interfered with a contraceptive method. If pregnancy occurs during the study, the outcome of the pregnancy will then need to be collected (post-study if necessary).

The subjects recruited into this study are under the age of 18 years, however it is anticipated that most subjects will be pre-pubescent. A serum HCG pregnancy test will be performed on all female subjects of childbearing potential at screening, baseline/pre-conditioning assessment, before the administration of Busulfan, and before the administration of OTL-101. For females of child-bearing potential in whom preventive measures fail, pregnancies will be reported as indicated below.

In the event of any pregnancy reported in a participant no protocol treatment will be administered. Any subject who becomes pregnant during the study, before the administration of Busulfan or before the administration of OTL-101, will be withdrawn.

Information regarding pregnancies must be collected on the AE page of the eCRF and reported to the Sponsor as an SAE. The Sponsor will request further information from the Investigator as to the course and outcome of the pregnancy.

The Investigator must instruct all female subjects of reproductive age to use a medically approved method of contraception throughout study participation. The Investigator must also instruct all female/male subjects of reproductive age to inform them immediately should they/or their partner become pregnant during the study. The Investigator should counsel the subject, discuss the risks of a pregnancy and the possible effects on the fetus. Monitoring of the subject/the partner should continue until conclusion of the pregnancy, which may involve follow up after the subject's involvement in the study has ended.

If the Investigator becomes aware of a pregnancy occurring in the partner of a subject participating in the study, this should be reported to the Sponsor. After the partner has given written consent, she should be counselled and followed as described above. Monitoring of the partner should continue until conclusion of the pregnancy.

8.2.5 Deaths

All AEs resulting in death during the study period must be reported as an SAE within 24 hours of the Investigator's knowledge of the event.

The convention for recording death is as follows:

- Adverse event term: lead cause of death (e.g. multiple organ failure, pneumonia, myocardial infarction),
- Outcome: fatal.

The **only exception** is if the cause of death is unknown (i.e. sudden or unexplained death), in which case the AE term may be 'Death' or 'Sudden death'.

8.2.6 Discontinuation/Withdrawal due to Adverse Events/Serious Adverse Events

Discontinuation/withdrawal due to AEs should be distinguished from discontinuation/withdrawal due to an insufficient response to OTL-101.

If the subject withdraws from the study due to an AE/SAE, it must be reported immediately to the Sponsor's designated representative (see [Section 8.2.3](#)). In all cases, the Investigator must ensure the subject receives appropriate medical follow up.

8.2.7 Reporting to Competent Authorities/IECs/IRBs/Other Investigators

The Sponsor will ensure that processes are in place for the submission of reports of Suspected Unexpected Serious Adverse Reactions (SUSARs) occurring during the study to the CA, IEC/IRB and other Investigators concerned by OTL-101. Reporting will be done in accordance with the applicable regulatory requirements.

For the single study center in the US, SUSARs and other important safety reports, when appropriate, will be submitted directly to the Investigators. It is the responsibility of Investigators to notify their IEC/IRB and the FDA in a timely manner.

8.3 Physical Examination

Physical examinations, including weight (kg) and body height (cm) will be conducted at times indicated in [Table 1](#) and [Table 2](#).

Any clinically significant physical examination findings (abnormalities) observed during the study will be reported as AEs. Any physical examination findings (abnormalities) persisting at the end of the study will be followed by the Investigator until resolution or until reaching a clinically stable endpoint.

A review of all body systems will include the following:

- General appearance
- Skin
- Head, including ears, eyes, nose, throat, if feasible.
- Respiratory
- Cardiovascular
- Abdomen (including liver and kidneys)
- Neurological examination with sensory testing

Any abnormalities or changes in intensity noted during this review of body systems should be documented in the source document and reported appropriately in the eCRF. In addition, the resolution of any abnormal findings during the study will be noted in the source document and eCRF, if clinically significant.

8.4 Vital Signs

Vital Signs (including blood pressure, pulse rate, respiratory rate and temperature) will be conducted at times indicated in [Table 1](#) and [Table 2](#). Blood pressure and pulse will be recorded after five minutes of rest in a sitting position.

Any clinically significant values or deviations from baseline vital signs will be recorded as an AE.

8.5 Electrocardiograms

An ECG will be conducted at times indicated in [Table 1](#) and [Table 2](#).

A twelve-lead ECG will be recorded at a paper speed of 25 mm/sec so that the different ECG intervals (RR, PR, QRS, QT) can be measured manually/automatically. The ECG will be recorded [with the subject in supine position after five minutes of rest] until four regular consecutive complexes are available. Automated ECG interval estimates taken from the ECG recorder will be used in this study.

Any clinically significant abnormalities will be recorded as AEs.

8.6 Laboratory Safety Tests

Blood samples for serum chemistry and hematology, and a urine sample for urinalysis will be taken for evaluation of laboratory safety parameters listed in [Table 3](#) according to the times indicated in [Table 1](#) and [Table 2](#). All clinical laboratory assays will be performed according to the relevant laboratory's normal procedures. Reference ranges will be supplied by the laboratory and used to assess the laboratory data for clinical significance and out-of-range pathological changes.

For the evaluation of hematology and biochemistry panels, and urinalysis, the Investigator will review the safety laboratory test results, document the review, and record any clinically relevant changes occurring or observed during the study in the AE section of the eCRF. Changes compared to pre-harvest tests will be recorded as AEs if they are considered to be clinically significant by the Investigator.

All clinically relevant abnormal laboratory tests occurring during the study will be repeated at appropriate intervals until they return to baseline or to a value deemed acceptable by the Investigator and the Sponsor's clinical monitor (or his/her designated representative) or until the abnormality is explained by an appropriate diagnosis.

Table 3: Clinical Laboratory Tests

Hematology parameters	Biochemistry parameters	Urinalysis
Red blood cell (RBC) count	Blood Urea Nitrogen	pH
Hemoglobin	Creatinine	Glucose
Hematocrit	Total bilirubin	Ketones
Mean corpuscular volume (MCV)	Sodium	Protein
Mean corpuscular hemoglobin (MCH)	Potassium	Bilirubin
Mean corpuscular hemoglobin concentration (MCHC)	Chloride	Blood
White blood cell (WBC) count with differential;	Calcium	Urobilinogen
Neutrophils	Aspartate transaminase (AST)	Nitrites
Lymphocytes	Alanine transaminase (ALT)	Leukocytes
Monocytes	Alkaline phosphatase (ALP)	Specific gravity
Eosinophils	Albumin	
Basophils	Total protein	
Platelet count	Glucose	
Coagulation parameters	Magnesium	
Prothrombin time (PT) or partial thromboplastin time (PTT) and internal normalised ratio (INR)	Phosphates	

